Primary Aim: To determine if a 48 hour maximum dwell time reduces bacterial contamination and biofilm formation of feeding tubes, feeding tube hubs, and intraluminal fluid in premature VLBW infants. **Primary hypothesis**: Feeding tubes which remain in place 0-48 hours will have less contamination and less biofilm formation compared to those left in place for 7 days.

Aim 2: Compare gastrointestinal microbial dysbiosis and inflammation between Group 1 and Group 2. **Hypothesis:** Infants in Group 1 will have less GI microbial dysbiosis and inflammation compared to Group 2.

Aim 3: Determine the effect of feeding tube dwell time and feeding tube contamination, and biofilm formation on selected health outcomes in premature VLBW infants. **Hypothesis:** Infants in Group 1 will have lower odds for necrotizing enterocolitis and late onset sepsis, and improved nutritional outcomes compared to Group 2.

5. Research Plan:

A randomized controlled trial will be conducted to determine whether feeding tube dwell time is associated with level of feeding tube contamination. Infants will be randomly assigned to have their feeding tubes removed at 0-48 hours or 7 days for the first 4 weeks of life. The feeding tube lumen, interluminal liquid and hub will be analyzed for level of contamination.

Sample and Setting

The proposed study will follow a prospective cohort (N =151) premature VLBW male and female infants for 4 weeks following birth. If the mother is providing breast milk to her infant, she will also be included in the study since she will be providing 2 samples of her breast milk for analysis.

Inclusion criteria are: 1) be born to a mother who is at least 18 years of age and English or Spanish speaking, 2) born at \leq 30 weeks 3) have a birthweight \leq 1500 grams, 4) be born to a mother who is COVID Negative, 5) have a feeding tube placed within 24 hours of birth and 5) be expected to require a feeding tube for 4 weeks following birth.

Exclusion criteria are: 1) Infant with known congenital GI anomalies, (2) are not expected to live, or (3) Infants will be withdrawn from the study if they require abdominal surgery for GI morbidities.

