Sample Size Determination/Power Analysis: The primary aim of this study is to test for associations between feeding tube dwell time and the bacterial load present in the feeding tube. Pilot study results were used to estimate variance for the log transformed values of bacterial load observed in cultures. The study employs a repeated measures design, with measurements performed on each neonate each week of the 4 week study duration. For the primary bacterial contamination aim, each measurement consists of measures from 5 individual feeding tube sections for 5 individual colony types, providing a total of 100 within-subjects data points per neonate. Given the repeated measures design and the incorporation of selected covariates, a Generalized Linear Mixed Model (GLMM) analysis is planned for the primary aim. The data derived from the pilot study of 31 feeding tubes informed the covariance structure and means vectors for entry into PASS 14's procedure which estimates mixed models power using simulation. Using a .005 level of significance (in recognition of the multiple inferential tests), 400 simulation samples, a minimum detectable difference of 3.0 (natural log transformed colony forming units), and employing the pilot data to inform mean vectors and the unstructured covariance matrix for the simulations, the lower 99% confidence limit for power is .97 for the Dwell Group by Colony Type interaction, which is of primary interest. To accommodate the anticipated 10% loss due to surgery or death, 134 neonates will be enrolled. If mothers are providing breast milk samples, 151 mothers would also be enrolled.

Standard Infant Feeding Protocol

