As per standard NICU protocol, all infants will begin receiving TPN within 24 hours of life. In addition, all infants will have an orogastric (OG) or nasogastric (NG) tube placed upon admission to the NICU and begin receiving some enteral feeding within 72 hours. Length of insertion of the OG/NG tube is determined by measuring from the tip of the nose to the tip of the ear lobe and then halfway between the xyphoid process and umbilicus (Ellett et al., 2011). Minimum insertion length based on the weight of the infant (Cordero et al., 2011). If the infant receives an X-ray upon admission, placement of the OG/NG tube is verified. Placement is also verified if additional X-rays are taken during the study as per usual OG/NG placement protocol in the NICU. Depending on the infant's gestational age, weight, and clinical status, feedings are initiated at up to 20mL/kg/d and advanced daily by no more than 20mL/kg/d toward a goal of 120-150mL/kg/d divided into 8 equal feedings per day using the established University of Florida Children's Hospital NICU feeding guidelines. If mothers own breast milk is unavailable, infants will be provided donor breast milk as per NICU standard care.

Consent Process

Within 72 hours of life, and within 24 hour of initiating feeds of \leq 20 mL/kg/d, informed consent will be obtained from the mother either in her hospital room or the NICU. The PI or research coordinator will ask the mother's or infant's nurse whether the mother is willing to speak with someone regarding enrolling her infant in a research study. If the mother says yes, the PI or research coordinator will explain the study and invite the mother to have her infant enrolled. All questions will be answered and mothers will be provided ample time to discuss with family and friends. If the mother consents and is providing breast milk to her infant, she will also be consented since will be providing 2 samples of breast milk for analysis

Breast Milk Feedings

Current practice in this NICU is to provide donor breast milk to all infants born prior to 30 weeks until they are 32 weeks post conceptual age. For this study, all infants will receive either mother's own breast milk or donor human milk for the 4 week study. If the infant is scheduled to be discharged prior to 4 weeks, the infant will be transitioned to formula as per NICU standards.

Procedure

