Following consent, data including gestational age, chronologic age, birth weight, race, gender, date and time of sample collection, feeding tube dwell time, duration of antibiotic therapy since birth, episodes of sepsis, other medications, mode of delivery, and mode and type of feeding will be obtained from the EMR. Other data including incidence of stage 2 or greater necrotizing enterocolitis; episodes of presumed or culture proven late onset sepsis (occurring > 3 days of life); days to discharge; nutritional outcomes, including weekly enteral intake, days to full enteral feedings (120 mL/kg/d),(150ml/kg/day), hours of parenteral nutrition, evidence of PNALD (level of direct bilirubin, alkaline phosphatase, aspartate aminotransferase (AST) and alanine aminotransferase (ALT); growth indices (weekly weight, head circumference and length); and hours with a central venous line will be collected.

Infants in both groups will have a bedside sign and EPIC note stating which group they are assigned to and when they are scheduled for feeding tube replacement. Infants will have their feeding tubes replaced 0-48h (Group 1) and every 7 days (Group 2). At the designated time, the feeding tube will be replaced by either the bedside nurse or the research coordinator (an experienced NICU nurse) using the NICU's standard method of feeding tube insertion.

All tubes will be adhered to the infant's face using the same procedure designed to decrease the risk of feeding tube dislodgement and protect skin integrity. The method of tube securement will be approved by NICU management/staff and comply with NICU skin care guidelines. The orogastric tubes will be taped to the chin from the middle of the mouth and nasogastric tubes will be taped under the lateral edge of nares. The research team will check the security of the tube adherence 3x per week and re-secure as necessary. On the day that the study feeding tube is scheduled to be removed, the research coordinator will coordinate with the bedside nurse when the feeding tube will be removed and replaced. In the event the infant has a Replogle tube instead of a feeding tube on lab collection day, the Replogle tube will collected. At the designated time, the feeding tube or Replogle will be removed and immediately placed in a sterile Ziploc bag and placed on ice for immediate transfer to laboratory by member to research team.

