Data integrity will be evaluated using descriptive statistics (e.g.: means, standard deviations, frequencies, percents, range) appropriate for measurement level. Checks for implausible or outof-range values, distributional forms, the presence and distribution of censored values (e.g.: inflammatory markers), and missingness will be performed. Data transformations (e.g.: Box-Cox family of transforms) will be made, if required, based on evaluation of model fit and tenability of assumptions. If applicable, regression techniques which can accommodate censored variables (e.g. MPLUS version 8 or higher)⁵⁸ will be employed. Selected variables (e.g.: type of feed (mother's breast milk or donor breast milk), whether NPO, antibiotic use, gestational age, chronological age, gastric pH and sex) will be screened for potential inclusion as covariates in each of the statistical models tested. Associations between each potential covariate and the respective dependent variable will be examined, and only those variables having a p<.10 association and whose inclusion improves model fit will be retained. The general modeling strategy will be a generalized linear mixed model (GLMM) approach. A GLMM is able to accommodate different numbers of measurements between subjects, utilize data from subjects when some of the data is missing (that is, subjects with some missing data points will not be dropped from analysis), can incorporate time-varying covariates, flexible covariance structures, and a variety of dependent variable distributions (including dichotomous), and thus will be able to accommodate the analyses proposed. Model fit and strength of association will be evaluated using Vonesh's GOF macro for SAS. Our primary goal will be to assess differences in marginal least squares means between the dwell time groups. All analyses will be performed using SAS software version 9.4 or later. Statistically significant interaction effects will be evaluated using simple main effects analyses via the SLICE option available in the SAS/STAT GLMM procedures. Due to the number of inferential tests planned, it is not practical to maintain a 5% experiment-wise Type I error rate; however, significance levels will be adjusted to maintain a model-wise 5% Type I error rate through use of a Benjamini-Hochberg approach.

Data Entry and Management

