A code key stored separate from the data set will be used. The code key will be kept in a locked cabinet in the research office. All data will be entered into a REDCAP database having integrated data quality and consistency checks. The study database created in REDCap will be password-protected and housed on a designated database server. Data quality will be monitored and assured as reported and as entered into the database. All hardcopy forms will be

Variable	Measurement	Timing
Descriptive (1-2) below		
1. Maternal, prenatal and perinatal demographics	Maternal history, prenatal and perinatal complications and medications, mode of delivery, antibiotic use, steroid use	Collected upon entry into study.
2. Infant demographics	Race/ethnicity, sex, gestational age, birth weight, Apgar scores, resuscitation at birth and neonatal acuity (SNAP II) score, type of feeding, whether or not the infant is NPO, medications effecting gastric pH, chronologic age, NPO, number of days and type of antibiotics	Collected upon entry into study and during the 4 week study period. Antibiotic data tracked for 6 weeks
Microbial analysis of feeding tubes, feeding tube hubs and residual intraluminal liquid Analysis of gastric contents (1-2)	Culture based analysis and microbial analysis (16S rRNA and metagenomics sequencing). Presence of biofilm in feeding tube or Replogle tube	Following removal of each feeding tube for 4 weeks
below		
1. Microbial analysis	16S rRNA and metagenomics sequencing	Weekly for 4 weeks
2. Inflammatory markers	Analysis of inflammatory markers	Weekly for 4 weeks
3. pH testing	Measuring acidity	Initially and weekly for 4 weeks
Analysis of stool (1-2) below		
1. Microbial analysis	16S rRNA and metagenomics sequencing	Weekly for 4 weeks
2. Inflammatory markers	Analysis of inflammatory markers	Weekly for 4 weeks
3. pH testing	Measuring acidity	Weekly for 4 weeks
Nutritional outcomes (1-6) below		
1. Enteral intake	24-hour enteral feeding intake in mL/kg	Daily for 6 weeks
2. Time to full feeds	First day infant received ≥120 mL/kg/d of enteral feedings. First day infant received 150ml/kg/d	Recorded daily until 150 mL/kg/d reached (up to 6 weeks)
3. Hours of PN	Number of hours infant received some parenteral nutrition	Daily for up to 20 weeks

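### The plan withdraws infants who need abdominal surgery from the study but does not say whether their Aim 3 outcomes are still collected, or which infants Aim 3 analyses

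*Combined protocol and SAP*

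**What the plan says.** Under Exclusion criteria in section 5 (Research Plan), the plan lists an event that can only happen after enrolment: "Infants will be withdrawn from the study if they require abdominal surgery for GI morbidities". The sentence names the study as a whole and gives no time window. The Sample Size Determination/Power Analysis paragraph treats the same event as attrition: "To accommodate the anticipated 10% loss due to surgery or death, 134 neonates will be enrolled".

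Aim 3 compares the randomised groups on clinical outcomes: "Infants in Group 1 will have lower odds for necrotizing enterocolitis and late onset sepsis, and improved nutritional outcomes compared to Group 2". The Procedure section collects "incidence of stage 2 or greater necrotizing enterocolitis". The data table under Data Entry and Management counts NEC shown on radiology or at surgery. Its follow-up periods are:

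- NEC, late onset sepsis, PN hours and central line hours: up to 20 weeks.
- Length of stay: to discharge.
- Enteral intake and time to full feeds: up to 6 weeks.
- Growth: daily for 4 weeks, plus a value at discharge.

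On incomplete data, Statistical Analysis says of the mixed model that "subjects with some missing data points will not be dropped from analysis". No section names an analysis set for Aim 3, and none says what happens to outcome data after a surgical withdrawal.

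**The concern.** Surgery for a GI morbidity can be a consequence of NEC, and NEC is an Aim 3 endpoint. If withdrawal ends data collection, follow-up stops because of an event on the causal path that the trial hypothesises, and the arms may differ in how often that happens. The infants affected are likely to be among those with the most to record afterwards: further sepsis, long PN and line use, poor growth and a long stay.

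PN and line hours are running totals. An infant whose record stops at surgery would show a short total where the true one may be long. A mixed model uses what was recorded; it cannot supply events or a length of stay that nobody recorded. If withdrawn infants are instead left out of the analysis, Aim 3 no longer compares the groups as randomised. Aim 3 carries the trial's clinical claim, so the handling of these infants should be fixed in advance.

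**Working it through.** **1. The plan's own loss figure.** The plan gives 134 enrolled with 10% loss. 120 / (1 − 0.10) = 133.3, which rounds up to 134, so the figure fits an evaluable sample of 120. The plan does not state that base. Expected losses are 134 × 0.10 = 13.4 or, with the cohort of 151 given under Sample and Setting, 151 × 0.10 = 15.1. Both counts include deaths, and the split is not given. The difference between 134 and 151 is a separate matter.

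**2. The two readings, side by side.**

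| Text | Points towards |
|---|---|
| Withdrawal rule: the study as a whole, no time limit | Collection ends |
| Sample size: surgery counted as loss | Collection ends |
| Sample and Setting: cohort followed for 4 weeks from birth | Study means the 4-week phase |
| Sample size: "with measurements performed on each neonate each week of the 4 week study duration" | Study means the 4-week phase |
| Breast Milk Feedings: "donor human milk for the 4 week study" | Study means the 4-week phase |
| Data table: refers to a 4-week study period and to 4 active weeks | Study means the 4-week phase |
| Data table: outcomes to 20 weeks or discharge | Follow-up outlasts that phase; silent on withdrawn infants |

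The narrower reading is plausible, but it is never stated. Even if the rule applies only to surgery in the first 4 weeks, those infants' later outcomes and their place in the denominator remain undefined.

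**3. Illustration for a mean (PN hours).** The documents give no surgery rate, so every rate here is an assumption: 67 infants per arm (134 split 1:1), surgery in s1 = 3% of Group 1 and s2 = 7% of Group 2 (67 × 0.03 = 2.0 and 67 × 0.07 = 4.7 infants), and E = 1 to 3 SD more PN hours per surgical infant.

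- Shift in the Group 2 minus Group 1 difference when these infants are removed: (s2 − s1) × E = 0.04 × 1 = 0.04 SD to 0.04 × 3 = 0.12 SD.
- Standard error of the difference: √(2/67) = 0.173 SD, so the shift is 0.04/0.173 = 0.23 to 0.12/0.173 = 0.69 standard errors.
- Difference detectable with 80% power at two-sided 5%: (1.960 + 0.842) × 0.173 = 0.484 SD, so the shift is 8% to 25% of it.
- Equal surgery rates give 0; 7% v 3% reverses the sign.
- If infants are kept but each total is cut short by D SD, the shift is (s2 − s1) × D, so the same figures apply for D of 1 to 3.

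**4. Illustration for the NEC odds ratio.** Assume NEC in 6% v 12% (Group 1 v Group 2), 67 per arm, and consider only surgery for NEC. The true OR is (0.06/0.94)/(0.12/0.88) = 0.47. The SE of log OR is √(1/4.02 + 1/62.98 + 1/8.04 + 1/58.96) = 0.64. Let f1 and f2 be the share of NEC cases that are surgical. Removing surgical cases multiplies the OR by (1 − f1)/(1 − f2).

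| f1 v f2 | Surgical NEC rate | OR, removed | OR, kept as non-events |
|---|---|---|---|
| 30% v 30% | 1.8% v 3.6% | 0.47 | 0.48 |
| 50% v 50% | 3.0% v 6.0% | 0.47 | 0.48 |
| 30% v 50% | 1.8% v 6.0% | 0.66 | 0.69 |
| 50% v 30% | 3.0% v 3.6% | 0.33 | 0.34 |

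For unequal shares the shift on removal is ln(0.7/0.5) = 0.336, or 0.336/0.637 = 0.53 standard errors, in either direction. If the triggering episode and the infant stay in the analysis, the OR does not move.

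**The case against.** The best defence is that the study means the 4-week tube and sampling phase, as several sections suggest, and that the 20-week rows of the data table apply to every enrolled infant. That may well be what was intended. It stands as a reason for caution, but not as an answer, because no text says so.

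A second defence is that the withdrawal rule and the NEC row do not contradict each other: an episode can be recorded and then lead to withdrawal. This stands. A reader might infer that surgical NEC is bound to vanish from the count; the documents do not support that.

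A third is that the mixed model keeps infants with partial data. This points against wholesale removal, but the sentence does not mention withdrawn infants, and the model cannot restore outcomes that were never collected.

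A reader might also infer that the arm with more surgery always looks better than it is. That holds for a mean such as PN hours under the assumptions above, but not for the NEC odds ratio. In the last row of the table Group 1 has less surgery (3.0% v 3.6%), yet its OR moves from 0.47 to 0.33 and its benefit is overstated. On removal, what matters is the difference in the surgical share of NEC cases.

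Finally, consent pages are not in the public document and may deal with data use after withdrawal.

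**Conclusion.** The concern holds as a gap in the plan that, followed literally, loses Aim 3 outcomes because of an event related to an Aim 3 endpoint. The outcomes most exposed are those after surgery: later sepsis, PN and line hours, growth and length of stay. Whether the infant stays in the denominator is also open.

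The size and direction of any bias cannot be determined from the documents. The illustrations rest wholly on assumed rates. They stay below one standard error (0.23 to 0.69 for PN hours, 0.53 for NEC on removal) and fall to zero or nearly zero when the arms have equal surgery rates or equal surgical shares. The 13 to 15 expected losses are a planning figure that includes deaths; the number of surgical withdrawals could be lower or higher.

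It would go too far to conclude that the rule certainly runs to 20 weeks or that the trial's main result is compromised. The primary contamination aim is less directly affected, and its sample size is not in question here.

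**What to change.** Reconcile the withdrawal rule under Exclusion criteria with the outcome rows of the data table:

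- State that surgical withdrawal does not end collection of the outcomes already planned from the medical record, which continue to their stated end points, subject to what consent allows.
- State that the NEC episode that led to surgery, and all earlier data, are kept.
- Name the Aim 3 analysis set: all randomised infants, in their assigned group.

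If the narrower reading was always intended, one sentence can settle the collection question; the analysis set still has to be named. Whether and when the assigned tube schedule stops after surgery is a clinical matter for the sponsor, and nothing is proposed on it here.

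The cost is a short protocol edit, a check of the consent wording, and a small amount of extra abstraction of fields already planned, for roughly 13 to 15 infants on the plan's own figure, deaths included.

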Title: Optimal Feeding Tube Dwell Time in VLBW Infants to Reduce Feeding Tube Contamination

NCT03728608

Date: 2/15/2024

Protocol

4. Background:

The long-term goal of this research is to improve short and long-term health outcomes for premature infants in the NICU by decreasing complications caused by contaminated feeding tubes such as sepsis, pneumonia and feeding intolerance. Because premature infants in the NICU may be too immature or ill to orally feed, a feeding tube is required to meet their nutritional needs. These feeding tubes have been shown to be a reservoir for pathogenic and often antibiotic-resistant bacteria and are thus a risk to neonatal health.

Contaminated feeding tubes are a conduit for bacterial migration into the stomach and intestines leading to gastrointestinal pathogenic bacterial overgrowth, abnormalities in pro-inflammatory cytokine response and increasing the risk of late onset sepsis, necrotizing enterocolitis and feeding intolerance. Feeding tubes also disrupt the oral microbiota increasing pathogenic mouth bacterial and the risk of pneumonia. The critically ill infant's significantly suppressed immunity, impaired intestinal barrier function and lack of beneficial gastrointestinal bacteria place them at tremendous risk of morbidity related to feeding tube contamination.

Contamination of medical devices such as feeding tubes is related to length of time the device remains in place (dwell time). In the NICU, universal guidelines regarding feeding tube dwell time are non-existent and feeding tube replacement is often delayed for weeks following insertion. The optimal feeding tube dwell time to reduce or prevent contamination and its associated morbidity is currently unknown. In addition, the optimal feeding tube dwell time to avoid abnormal bacterial colonization of the stomach and intestines and the extent to which contamination of these domains relate to adverse neonatal health outcomes is unknown. Thus, the primary purpose of this study is to determine if a maximum feeding tube dwell time of 48 hours reduces contamination compared to a feeding tube dwell time of 7 days, thereby improving neonatal health outcomes.

Aims include the following:

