Metagenomic analyses. For metagenomic data production, libraries will be constructed for each section of the feeding tube at the Interdisciplinary Center for Biotechnology Research at the University of Florida (ICBR). Libraries will be sequenced on the Illumina HiSeq 2500 platform, targeting ~3 Gb of sequence per sample with 100 bp, paired-end reads. Profiling of metabolic pathways will be performed using with Blast2GO at https://www.blast2go.com. To identify genes encoding proteins with potential antibiotic resistance functions, the metagenomes will be analyzed using ResFinder 2.1. The ResFinder program

(http://cge.cbs.dtu.dk/services/ResFinder/) is an acquired antimicrobial resistance search tool which identifies genes with > 40% identity to known antibiotic resistance genes to identify genes encoding proteins with potential virulence functions will be used VirulenceFinder 1.5 (http://cge.cbs.dtu.dk/services/VirulenceFinder/). Using this tool curated by the Center for Genomic Epidemiology we will be able to identify virulence factors associated with adherence,

toxin production, exoenzymes, host immune evasion, and secretion. Based on the findings of the metagenomic data, the antibiotic susceptibility of bacterial isolates will be confirmed by antimicrobial susceptibility tests using the Kirby-Bauer method.

To determine bacteria in the feeding tube which may originate from the mother's breast milk or donor milk, a small sample will be obtained at week 1 and week 4 and similar 16S rRNA and metagenomics sequencing will be performed. If still providing breast milk to their infant, the infant's mother will be asked to provide 2-5 ml of her breast milk which she has pumped per standard NICU policy. This sample will be analyzed using similar microbiome and metagenomic analyses.

Biofilm Analysis. The presence of biofilm in the interior surface of the feeding tubes will be determined using fluorescent stains and visualized by confocal microscopy. We will utilize a variety of fluorophores to discriminate live/dead cells (FilmTracer LIVE/DEAD biofilm viability kit, Invitrogen) and the matrix components (FilmTracer SYPRO/Ruby biofilm matrix stain, Invitrogen) as directed by the manufacturer. The results obtained will be confirmed by scanning electron microscopy (SEM).

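### The only power figure (.97) is for the dwell-group by colony-type interaction, while the hypothesis and the stated analysis goal are a dwell-group difference

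*Combined protocol and SAP*

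**What the plan says.** Section 4 (Background) gives the primary purpose as to "determine if a maximum feeding tube dwell time of 48 hours reduces contamination compared to a feeding tube dwell time of 7 days". The Primary Aim pairs this with biofilm: "To determine if a 48 hour maximum dwell time reduces bacterial contamination and biofilm formation of feeding tubes". The primary hypothesis is directional: "Feeding tubes which remain in place 0-48 hours will have less contamination and less biofilm formation" than tubes left for 7 days. None of these statements mentions colony type.

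Sample Size Determination/Power Analysis opens by restating the aim as an association between dwell time and bacterial load. It says that "each measurement consists of measures from 5 individual feeding tube sections for 5 individual colony types", which over 4 weeks gives 100 values per infant. Power was simulated at alpha .005 with 400 samples, a difference of 3.0 in natural-log CFU, and pilot means and covariance. The result is that "the lower 99% confidence limit for power is .97 for the Dwell Group by Colony Type interaction, which is of primary interest". No other power figure is given.

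Statistical Analysis sets a general GLMM strategy for all outcomes and states: "Our primary goal will be to assess differences in marginal least squares means between the dwell time groups". Significant interactions are followed by SLICE simple-effect tests. Benjamini-Hochberg is said to keep a 5% Type I error rate within each model.

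On biofilm, the Biofilm Analysis paragraph says: "The presence of biofilm in the interior surface of the feeding tubes will be determined using fluorescent stains". The power section does not mention it.

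**The concern.** The interaction asks whether the dwell effect differs between colony types. The hypothesis asks whether the 48-hour group has less contamination. These are different questions, and the power section and the analysis section each call a different one primary.

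Two things are at stake. A reader will take .97 as assurance that the trial can answer its main question, and it gives no such assurance. In addition, the interaction, the marginal difference and the colony-type slices can disagree, and the plan does not say which of them confirms the primary hypothesis. That leaves room to choose among them once results are known. The unstated rank of biofilm adds to this.

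**Working it through.** **The plan's own figure.** The .97 cannot be recomputed, because the pilot mean vectors, the covariance matrix and the evaluable N are not given. It is plausible in itself. With 400 simulations, 396 or 397 successes give exact 99% lower limits of .969 and .973; a Wald limit near .97 needs 394 or 395. The point estimate of interaction power is therefore about .985 to .993.

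**Inputs.** From the plan: 134 enrolled, 10% loss, alpha .005, difference 3.0, five colony types. 134 × 0.9 = 120.6, so about n = 60 per arm. Assumed: 1:1 allocation, one mean per infant and colony type, a common SD *s*, equal correlation ρ between types, and the effect patterns below.

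**Formulas.**
- Interaction: parallelism test, F(4, 2n − 5) = F(4, 115). For a difference of 3.0 in k of 5 types, ncp = (n/2)(9k − 9k²/5) / (s²(1 − ρ)). Power .97 needs ncp = 31.2.
- Overall dwell-group difference: two-sided t test, 118 df, difference 3k/5, variance of the infant mean s²(1 + 4ρ)/5.

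**Case 1: the same 3.0 reduction in all types** (s = 3, ρ = .3). With k = 5, 9k − 9k²/5 = 45 − 45 = 0, so the interaction is rejected at its alpha, 0.5%. The infant-mean SD is √(9 × 2.2/5) = 1.99 and the t non-centrality is 3/(1.99 × √(2/60)) = 8.3, so overall power is about 100%.

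**Case 2: opposite effects** (+3 in one type, −3 in another; between-infant/within-type SDs from 2/3 to 4/4, simulated). Interaction power is .98 to 1.00, while the overall difference is rejected only at about the alpha level (.003 to .008).

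**Case 3: interaction power fixed, 3.0 in k of 5 types.** Example with k = 1, ρ = .3: s² = 30 × 7.2/(31.2 × 0.7) = 9.89; the overall difference is 0.6; the infant-mean SD is √(9.89 × 2.2/5) = 2.09; the non-centrality is 0.6/(2.09 × 0.1826) = 1.57; power is .10. The other cells follow in the same way. The second figure in each cell sets interaction power at .993 (ncp 38.4) instead of .97.

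| Types affected | ρ = 0 | ρ = .1 | ρ = .3 | ρ = .5 |
|---|---|---|---|---|
| 1 | .48 / .60 | .27 / .36 | .10 / .14 | .05 / .06 |
| 2 | .95 / .985 | .78 / .88 | .39 / .50 | .16 / .22 |
| 3 | 1.00 / 1.00 | .995 / .999 | .84 / .92 | .48 / .60 |

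With one affected type at interaction power .97, the within-type contrast has power >.999, .999, .99 and .94 across the same correlations. A low overall power can thus sit beside a high colony-type power.

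**Case 4: 3.0 is the overall difference.** Power is .995, .89, .66 and .45 for an infant-level SD of 3, 4, 5 and 6.

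**Benjamini-Hochberg** (independent tests, real effects always detected). The smallest null p-value among m₀ nulls in m tests is rejected at or below .05(m − m₀ + 1)/m. The chance of any false rejection is at least:
- 2 of 5 null: 1 − .96² = .078
- 3 of 5 null: 1 − .97³ = .087
- 5 of 10 null: 1 − .97⁵ = .141

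Rejections at later ranks add very little. With all 5 null, simulation gives about 5%. Holm stays at or below about 5% in all these cases.

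**The case against.** The best defence is that the two sections form an ordinary sequence: test the interaction, slice if it is significant, otherwise read the marginal means. Statistical Analysis does name a dwell-group contrast, and the GLMM can estimate it. This stands as far as it goes. It would be wrong to say that the plan contains no dwell-group contrast or that the choice is wholly open; the defect is a conflict among a few named contrasts. But that paragraph is a general strategy for every model. It does not say which result confirms the primary hypothesis, and it disagrees with the power section about what is primary.

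A reader might also infer that biofilm has no analysis. The documents do not support that: it is recorded as presence, and the general GLMM strategy covers dichotomous outcomes. What it lacks is a rank and a power statement.

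It is fair to object that the .97 is a lower confidence limit, so calibrating to it makes the other powers pessimistic. The second figures in the table allow for this; the range hardly moves. It is also fair that the SDs, correlations and patterns are assumed, and that the pilot-based simulation need not have used such patterns. The figures illustrate; they do not estimate this trial's power.

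The Benjamini-Hochberg remark is a separate wording matter. The number of tests per model is not stated, and the excess over 5% arises only when some effects in the model are real.

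**Conclusion.** The point holds as an inconsistency that should be fixed. The power section and the analysis section name different primary tests, and the one power figure belongs to the test that does not address the hypothesis. That a uniform effect leaves the interaction null follows from algebra and needs no assumption.

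The tempting stronger conclusion, that the trial is underpowered, is not supported. Under the stated assumptions (60 per arm, alpha .005, assumed SDs, correlations and patterns), interaction power of .97 to .993 fits overall dwell-group power anywhere from about .05 to 1.00. Where the effect sits in one colony type, the slice for that type can be well powered. The documents give no SD and do not say whether 3.0 is a marginal, colony-type or other difference, so adequacy is neither shown nor refuted.

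Biofilm's missing rank and power, and the description of Benjamini-Hochberg as Type I error control (about 8 to 14% chance of any false rejection in the assumed cases), are smaller points.

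**What to change.** - Reconcile the two sections by naming one deciding dwell-group analysis for bacterial load at one stated alpha. Either use the marginal least-squares mean difference in ln CFU, with the interaction and slices secondary, or use pre-specified colony-type contrasts and align the primary hypothesis to them.
- State which contrast the 3.0 applies to. Re-run the existing simulation for the named contrast at the evaluable N, and report that power in place of .97.
- State whether biofilm is co-primary or secondary.
- Describe Benjamini-Hochberg as 5% false-discovery-rate control within each model, or use Holm if 5% Type I error per model is intended.

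The cost is wording plus one simulation run with the pilot inputs already in hand. The restated power may be less favourable than .97, a co-primary biofilm outcome would need its own power statement, and Holm gives up some power.
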